2.2. Trial Endpoints and Assessments

The Exploratory Trial Objectives are:

1. To assess the feasibility of 3-monthly follow-up visits, as a possible schedule for post-licensure vaginal ring clinical follow-up
2. To explore the correlation between drug concentrations and results from the visual inspection of the returned vaginal rings by research staff between the monthly and 3-monthly research centre follow-up schedules
3. To determine the proportion of participants electing to undergo HIV rapid tests at the research centres between scheduled 3-monthly visits
4. To characterize the IPM 027 participants who decline enrollment into IPM 032 (Decliner Population)
5. To explore self-reported acceptability of and adherence to the 25 mg Dapivirine Vaginal Ring-004.

The exploratory endpoints are:

- Feasibility of 3-monthly clinical follow-up schedule
- Dapivirine residual amounts in returned used vaginal rings and/or dapivirine concentrations in blood and/or vaginal fluid in correlation with results from the visual inspection of the returned used vaginal rings by research staff
- Proportion of participants opting for HIV rapid tests at the research centre between scheduled 3-monthly research centre follow-up visits
- Characteristics of IPM 027 participants who decline enrollment into IPM 032 (Decliner Population) and reasons for declining
- The proportion of women who report the use of the vaginal ring as acceptable
- Participant self-reported patterns of ring use

The exploratory endpoints will be assessed through:

- Participant report of feasibility regarding a 3-monthly clinical follow-up schedule (Participant Questionnaire)
- Number of women opting not to receive two additional rings at the 3-monthly visits
- Proportion of returned rings (used and unused) during the 3-monthly clinical follow-up schedule
- Dapivirine residual amounts in returned used vaginal rings and/or dapivirine concentrations in blood and/or vaginal fluid

- Visual inspection of the returned used vaginal rings by research centre staff
- Number of participants undergoing HIV rapid tests at the research centre between scheduled 3-monthly research centre follow-up visits
- Questionnaires and qualitative data regarding reasons for declining participation, ring acceptability and self-reported patterns of ring use.

5.16 Qualitative Behavioural Assessments

Each research centre will conduct two to three in-depth individual interview (IDIs) with approximately six participants in each of the following categories:

- Decliner Population
- Ring Users
- Ring Non-users

In cases of interest IDIs will be conducted; approximately three participants will be interviewed per site. These cases of interest may include, but will not be limited to participants who may have experienced social harms, may have had problems using the ring, or who HIV seroconverted

Focus group discussions may also be conducted with the above mentioned groups. Efforts will be made to ensure the sample size is representative of both previous IPM 027 participants as well as the two ring-naïve cohorts of women. Additionally, IDIs and/or FGDs with approximately six males from the community and/or male partners will be conducted at each research centre.

DVR-naïve participants will complete a behavioural questionnaire at enrolment, in addition to the participant questionnaire collected at other trial visits.

These assessments will provide data on acceptability and influencers of ring use. The recruitment and sampling strategy will be specified in the study operations manual.

8.4.5 Other results from Qualitative/Quantitative Behavioural assessments

Each research centre will conduct two to three in-depth individual interviews (IDIs) with approximately six participants in each of the following categories:

Decliner Population

Ring Users

Ring Non-users

In cases of interest IDIs will be conducted; approximately three participants will be interviewed per site. These cases of interest may include, but will not be limited to participants who may have experienced social harms, may have had problems using the ring, or who HIV seroconverted. Focus group discussions may be conducted with the above mentioned groups. Efforts will be made to ensure the sample size is representative of both previous IPM 027 participants as well as the two ring-naïve cohorts of women. Additionally, IDIs and/or FGDs with approximately six males from the community and / or male partners will be conducted at each research centre.

DVR-naïve participants will complete a behavioural questionnaire at enrolment, in addition to the participant questionnaire collected at other trial visits.

8.5 Data and Safety Monitoring Board

Safety data from the trial will be evaluated by an independent Data and Safety Monitoring Board (DSMB). The first scheduled meeting will take place approximately six months after all research centres have been activated and thereafter at approximately annual intervals for the duration of IPM 032. Based on the review of the data, the DSMB is required to provide recommendations about continuation, pausing, termination or other modifications to the trial, including changes to the information provided to participants for obtaining their informed consent. An IPM 032 DSMB charter will describe the roles and responsibilities of the DSMB, its composition, data to be provided to the DSMB, the process for disseminating trial data to the DSMB, and the communication plan between the DSMB and IPM.

Deviation Category	Description	Classification	Comment
1	
Inappropriate enrolment
 
More than one Inclusion or Exclusion criterion not met.
 
Inclusion Criteria:
 
Inclusion criterion 1: Previously enrolled in the IPM 027 trial
 
Inclusion criterion 2: Available for all visits and consent to follow all procedures scheduled for the trial
 
Inclusion criterion 3: Using an effective method of contraception at the Enrolment Visit, and intending to use an effective contraceptive method for the duration of trial participation, unless post-menopausal with no history of menses for one year prior to screening.
 
Inclusion criterion 4: HIV-negative as determined by the HIV algorithm applied at Screening/Pre-Enrolment
 
Inclusion criterion 5: Willing to refrain from participation in another research trial using drugs, vaccines, medical devices and microbicides for the duration of the IPM 032 trial
 
Inclusion criterion 6: Willing to provide adequate locator information for trial retention purposes and be reachable per local standard procedures (e.g., by home visit or telephone; or via family or close neighbour contacts); confidentiality to be maintained
	
Major
 
Major
 
To review
 
Major
 
Major
 
Major
 
Minor
	

Deviation Category	Description	Classification	Comment
	Exclusion Criteria: Exclusion criterion 1: Investigational product use permanently discontinued in response to an AE (where the AE was considered related to investigational product) or safety-related concern while taking part in the IPM 027 trial	Major	
	Exclusion criterion 2: Participant self-report of taking post-exposure prophylaxis (PEP) within ≤ 2 months at Screening Visit Note: Participants may be enrolled after completing the PEP regimen and a negative HIV test was documented at least 2 months prior to screening for IPM 032	To review	
	Exclusion criterion 3: Currently pregnant, or currently breast-feeding	Major	
	Intends to become pregnant	To review	
	Exclusion criterion 4: Known drug abuse or alcohol dependence in the 12 months prior to screening	To review	
	Exclusion criterion 5: Participated in another research trial (other than IPM 027) using drugs, medical devices, microbicides or oral pre-exposure prophylaxis agents within 30 days prior to screening	To review	
	Exclusion criterion 6: Any new illness or condition(s), chronic condition(s) or abnormal laboratory finding(s) that, in the opinion of the investigator, might put the participant at risk, or interfere with the trial objectives or the	To review	

Deviation Category	Description	Classification	Comment
	participant's adherence to trial requirements		
2	Missed visit	To Review	
3	Visit completed outside of permissible windows	To review	
4	Informed consent process deviations	To review	Deviations will be discussed on a case-by-case basis, and the severity will be determined by the nature of the deviation. Absence of documented informed consent prior to trial related procedures will be considered major.
5	IP incorrectly dispensed and used by participant	Major	
	Expired IP dispensed and used by participant	Major	
	Quarantined/not fit for use IP dispensed and used by participant	Major	Occurrence and extent of temperature excursions, for example, to be evaluated on a case-by-case basis.
6	SAE not reported within 24 hours	Minor	For definition of PP population this would be considered minor (i.e. participant would not be excluded from PP population) as the deviation does not have effect on data).
	Multiple unreported AEs for the same participant	To be reviewed	
	Any non-serious AE leading to permanent discontinuation of the IP not reported within 48 hours	Minor	
	Seroconversion not reported within 48 hours	Minor	
	Pregnancy not reported within 48 hours	Minor	

Deviation Category	Description	Classification	Comment
7 Failure to discontinue (temporarily or permanently) IP use for whom it is indicated	HIV Seroconversion	Minor	For definition of PP population this would be considered minor (i.e. participant would not be excluded from PP population) as the deviation occurred after the seroconversion (endpoint).
	Pregnancy	Major	
	SAE or non-serious AE (including laboratory abnormality) indicating need for IP discontinuation	Major	
8 Inappropriate treatment/management of medical conditions and follow-up of AEs		To review	Deviation will be discussed on a case-by-case basis, and the severity will be determined by the nature of the deviation
9 Mishandled laboratory samples (including samples that have been collected, processed, stored or transported incorrectly)	Incorrectly labelled samples, resulting in redraw	Minor	
	Incorrect storage (e.g. loss of cold chain with loss of samples)	Minor	
	Incorrect sampling (preservative contamination)	Minor	
	Data not recorded, resulting in loss of data (tear strip weight not recorded; rapid test result not recorded on log)	Minor	
	Lost samples (storage/shipping)	Minor	
10 Missing or incorrectly timed trial procedures	Pregnancy tests not performed as per protocol schedule	To review	
	Other trial procedures not performed as per protocol schedule.	To review	

Deviation Category	Description	Classification	Comment
11	Conduct of additional non-study related procedures	To review	Deviation will be discussed on a case-by-case basis, and the severity will be determined by the nature of the deviation
12	Participant non-adherence to trial requirements	To review	
13	Participant withdraws her consent	Major	
	Participant tests HIV-positive according to the HIV-testing algorithm	Minor	
	Participant is lost to follow-up, i.e. the research centre is unsuccessful (following reasonable attempts as defined in the local SOP) in contacting participant or bringing the participant back to the research centre	Minor	
	If for safety reasons, the Investigator considers it in the best interest of the participant to discontinue her from the trial	To review	For laboratory values: Major in cases where investigator has indicated the findings to be related to IP.
	At the discretion of the Investigator, IPM, the relevant Institutional Review Board/Independent Ethics Committee (IRB/IEC), or the government health authority	Minor	
14	Other, specify	To review	

Version 1.0 compiled by:

[name], Clinical Physician
[name], Clinical physician

1. INTRODUCTION

This document serves as the Statistical Analysis Plan (SAP) for the supplementary virology analysis of the Dapivirine Vaginal Ring-004 (DVR-004) Phase IIIb open-label extension trial, IPM 032. Specifically, this document describes the process for identification of samples and statistical methods that will be used to analyze the data resulting from retrospective resistance testing using a unique molecular identifier (UMI) next generation sequencing (NGS) methodology¹⁻³, as well as phenotypic susceptibility analysis recombinant retroviral system⁴.

There are several advantages of the NGS method employed in this analysis over standard NGS methodologies. The current methodology uses UMI ‘barcodes’ built into polymerase chain reaction (PCR) primers, which allows sequences originating from the same human immunodeficiency virus type 1 (HIV-1) ribonucleic acid (RNA) template to be grouped and aligned. Building consensus sequences from these alignments provides improved control of PCR and sequencing error, PCR bias, and PCR recombination. The number of UMI with consensus sequences allows the depth of sequencing to be calculated based on the number of HIV-1 RNA templates sampled, which can in turn be used to estimate the sensitivity of the individual sample analysis using an adaptation of the Clarke and Carbon equation

$$[P=1-(1-f)^N]$$

where P = probability, N = number of sequences, f = fraction of sequences with variant]^{5,6} to obtain the proportion of a minority species that can be detected with 95% confidence. The assay has been validated to detect resistance-associated mutations (RAMs) down to 1% prevalence, subject to the number of consensus sequences (UMIs) observed. Despite the robust nature of the assay and the analysis of its results, the NGS analysis should still be considered as exploratory. Of note, clinical interpretation of these data remains challenging. In addition to technical challenges, there is an absence of cross-laboratory standardization of outputs and of accredited means for external quality assessment^{7,8}. In the absence of resolution of these issues, the clinical relevance of the increased sensitivity for detection of resistance-associated mutations using NGS remains unknown.

Templates for all tables and listings that will be used to present the virology results are also provided. These analyses will be described in an addendum to the IPM 032 Clinical Study Report (CSR).

Table shells and listing shells that will accompany the analyses are provided in a separate document of mock tables and listings (T&L) ([Appendix 1](#)). This document is viewed as supporting material for the analyses and will not require signature approval if formatting changes are made.

2. OBJECTIVE

The primary purpose of this analysis is to further address, with supplementary information, the secondary objective for trial IPM 032:

- To assess the frequency of HIV-1 drug resistance in women who acquire HIV-1 infection while using the DVR-004.

Specifically, the analyses will facilitate the description of:

- the prevalence of all variants detectable to a minimum prevalence of 1%, 5%, or 10% in reverse transcriptase (RT) at seroconversion using NGS.
- the fold-change (FC) in phenotypic susceptibility of virus at seroconversion to dapivirine, efavirenz, etravirine, nevirapine, and rilpivirine relative to a wild-type control.
- the findings in relation to the population-based genotyping results described in the IPM 032 CSR and the Phase III [Clinical Virology Report Version 4.0](#).

3. ANALYSIS POPULATIONS

3.1. Safety Population

The safety population includes all trial participants who were enrolled from the parent trial, IPM 027, and received and inserted at least one DVR-004.

3.2. Virology Population

The virology population includes all participants in the safety population who experienced seroconversion (either using HIV-1 Rapid test result algorithms or determined to have been HIV-1 infected while using the DVR-004 based on reverse sequential HIV-1 RNA PCR testing) during investigational product (IP) use except:

- Participants who were deemed to be HIV-1 RNA positive at the time of enrolment.
- Participants who seroconverted after last product use (ie, at the Exit Visit) and were not HIV-1 RNA positive at the last product use visit, ie, were infected after they discontinued product use.

The virology population will be the main focus of this analysis. Available data for any participants infected with HIV-1 prior to enrolment or after last product use will be listed and described separately. Phenotypic analyses will be performed only on samples obtained at seroconversion during DVR-004 use.

4. GENERAL STATISTICAL CONSIDERATIONS

4.1. Analysis Software

Statistical analyses will be conducted by an external service provider of the International Partnership for Microbicides (IPM) and will be reviewed by IPM and the University of Pittsburgh Virology Laboratory. The analyses will be performed using SAS® for Windows or Linux/Unix (Version 9.2 or higher, SAS Institute Inc., Cary, North Carolina, United States of America [USA]).

4.2. Planned Subgroups

As numbers are small, there are no plans to perform analyses in subgroups. Should individual outlier results be observed, additional relevant characteristics may be described from the IPM 032 CSR listings or listings from this addendum.

4.3. Data Used for Analysis

Next generation sequencing will be attempted for all available seroconversion samples from all participants in the virology population, although results showing sensitivity to detect viruses present only at >10.0% prevalence (ie, with detection of < 28 UMI) will be summarized, although, due to inadequate sensitivity, these results will not be used to infer the absence of NNRTI RAMs. Analyses will be performed with cut-offs set to include the detection of minority species present in at least 10.0%, 5.0%, or 1.0% of UMI.

Results showing sensitivity to detect only minority species present with > 10.0% prevalence (ie, UMI < 28) will be described individually.

Phenotypic susceptibility and NGS will be performed on plasma samples taken at the time of HIV-1 seroconversion \pm 14 days. Any results from other time points will be listed and may be discussed separately, but not included in summary analyses.

4.4. Methods for Handling Missing Data

While every effort will be made to minimize the amount of missing data, as this is a retrospective analysis, some degree of missing data associated with sample availability and participant consent, is expected. Numbers of missing analyses will be provided along with numbers of participants included in the analysis, and tests conducted with and without successful outcomes.

If the date of the last IP exposure (ie, last ring removal) is incomplete or missing, the following imputation will be made:

- when only the day is missing, impute with min (last ring insertion date + 28 days, last day of the month), else
- impute with last ring insertion date + 28 days.

This should be added in a footnote in the applicable tables/listings. If the date itself should be printed, the original (not the imputed) date should be printed.

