9.2 Primary Endpoint 2 – Adherence

Dapivirine residual levels in used rings will be determined for all participants receiving IP, as a measure of adherence to ring use. The data will be listed, summarised and presented graphically, as described below.

Dapivirine Residual Levels in Used Rings

All used vaginal rings that are returned to the research centres at each trial visit are collected and shipped at regular, pre-defined intervals to an analytical laboratory,

where the rings are analysed to determine the residual amounts of dapivirine in the rings.

For this trial, a reported ring residual level of > 23.5 mg dapivirine will be used as an indication of non-adherence to ring use over the 30-day period (± 7 days) that a woman was to keep the ring *in situ*. Based on the data from the Phase III program, the cut-off value of > 23.5 mg for dapivirine ring residual levels was shown to be a good measure of non-adherence to ring use, indicating no or very little ring use.

The following summaries and graphical presentations will be produced for these data:

- A summary of ring residual levels at each trial visit and at the time of seroconversion, the time of first HIV-1 RNA positive as well as the time of last HIV-1 RNA negative will be presented with standard descriptive statistics – presented overall, by IPM 027 treatment arm, and by research centre. Corresponding box plots will be prepared.
- A descriptive summary of the ring residual levels by trial visit and by category of residual amount (< 20 mg, $20 – 21$ mg, $> 21 – 22$ mg, $> 22 – 23.5$ mg, and > 23.5 mg). This summary will be prepared overall, by IPM 027 treatment arm and by research centre, with corresponding bar charts.
- A summary relating the ring residual levels to time intervals (in days) between consecutive ring replacements (< 23 days, $23 – 37$ days, $> 37 – 84$ days, and > 84 days). Corresponding box plots will be prepared.

Note: All summaries and graphical presentations will be produced for both uncorrected dapivirine ring residual levels (as reported by the analytical laboratory) and residual levels corrected for manufacturing and assay variability, unless otherwise specified.

The aforementioned graphical presentations will be repeated for the ring residuals from the IPM 027 and IPM 032 trials, and will be based only on the participants from IPM 027 who enrolled in IPM 032. However, only the uncorrected ring residual levels will be used.

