The number of days that the participant reportedly wore the ring is based on data captured in the Ring Insertion/Removal Log (RL) CRF and the EXP CRF at the scheduled visit and any preceding unscheduled visit between the current and the previous scheduled visit. The total number of days that the participant was expected to wear the ring is a calendar month (30 days) from the insertion date.

The self-reported adherence rates will be presented in the following categories:

- $\geq 90\%$
- $\geq 80\% \text{ to } < 90\%$
- $< 80\%$.

Summary tables with descriptive statistics will be presented for accidental ring expulsions and removals by the participant for reasons other than instructed by the research centre staff.

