XXX-XXXXXX	DDMMYYYY XX	XX	XXX	XXX	X.XXX	XXXX	X	Yes/No	YxxX (xx), YxxX (xx), YxxxX (xx),....
etc.									

(a) PIDs infected on enrolment indicated with "^a"; PIDs with seroconversion off DVR-004 use indicated with "^b".

(b) Days since seroconversion (negative values indicate evaluation prior to seroconversion).

(c) Days since first HIV-1 RNA detection.

(d) Visits indicated with a * are not within 14 days of the seroconversion time point.

(e) Reference sequence: HXB2 (accession number K03455-1).

The sequenced region contains RT amino acids 81 – 150, 152 - 212. NGS analyses are considered exploratory.

[Notes to programmer: Amino acids are listed in numeric order (Note e); choose appropriate markers for different populations (Note a).]

Listing 16.2.8.20.2
Next Generation Sequencing: Listing of Detected NNRTI Resistance-associated Mutations
Safety Population

PID (a)	Sample Date	Days (b)	Days (c)	Visit Day	Visit (d)	Number UMI with Consensus	Sample Sensitivity (%)	Number of Mutations	NNRTI RAMs (e)
XXX-XXXXXX	DDMMYY	XX	XX	XXX	Month XX/ Week XX	XXXX	X	X	YxxZ (xx), YxxZ (xx),....
XXX-XXXXXX	DDMMYY	XX	XX	XXX	Month XX/ Week XX	XXXX	X	X	None
XXX-XXXXXX	DDMMYY	XX	XX	XXX	Month XX/ Week XX	XXXX	X	X	No Test
etc.									

Table includes PIDS only if NNRTI RAMs were detected in NGS analysis.

(a) PIDs infected on enrolment indicated with ^{aa}; PIDs with seroconversion off DVR-004 use indicated with ^{bb}.

(b) Days since seroconversion (negative values indicate evaluation prior to seroconversion).

(c) Days since first HIV-1 RNA detection.

(d) Visits indicated with a * are not within 14 days of the seroconversion time point.

(e) Mutations reported according to Stanford HIVdb algorithm version 8.4 (see SAP).

The sequenced region contains RT amino acids 81 – 150, 152 - 212. NGS analyses should be considered exploratory.

[Notes to programmer: Amino acids are listed in numeric order (Note e); choose appropriate markers for different populations (Note a).]

Listing 16.2.8.20.4
Phenotypic Data: Listing of All Available Data
Safety Population

PID	Sample Date	NNRTI RAMs	Result ID	DPV		EFV		ETR		NVP		RPV	
				IC ₅₀ (nM)	FC (a)								
XXX- XXXXXX	DDMMYY	None	1	x.xx (x.xx)									
			2	x.xx (x.xx)									
			3	x.xx (x.xx)									
			Avg	(x.xx)	x.x								

etc.

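### With only the day of last ring removal missing, the virology addendum's imputation rule can return a date before the recorded removal month (minor; one clause corrects it)

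*SAP*

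**What the plan says.** The rule is in the virology addendum SAP, section 4.4: "If the date of the last IP exposure (ie, last ring removal) is incomplete or missing, the following imputation will be made". There are two branches. The first reads "when only the day is missing, impute with min (last ring insertion date + 28 days, last day of the month), else". The second, for everything else, reads "impute with last ring insertion date + 28 days". The section also asks that outputs print the date as recorded and not the imputed one.

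The main SAP sets the expected length of wear. Section 9.4.4 says the number of days a ring should be worn "is a calendar month (30 days) from the insertion date". Section 9.2 refers to "ring use over the 30-day period (± 7 days) that a woman was to keep the ring" in place, and tabulates residual levels by "time intervals (in days) between consecutive ring replacements", with classes of > 37–84 and > 84 days.

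Two places in the addendum depend on whether seroconversion fell during ring use. Section 3.2 states: "Phenotypic analyses will be performed only on samples obtained at seroconversion during DVR-004 use". In the Appendix 1 shells, footnote (a) to Listings 16.2.8.20.1 and 16.2.8.20.2 has "PIDs with seroconversion off DVR-004 use indicated with" a marker.

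**The concern.** When only the day is missing, the month and year of removal are known, and any sensible imputation should fall within that month. The cap at month end suggests that this was the intention, but only the upper half of the constraint was written. If insertion + 28 days falls before the recorded month, the minimum selects it and the known month is discarded.

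The 28-day figure is shorter than the plan's own expected wear of 30 days, so ordinary use can trigger the problem. By contrast, the month-known conventions for adverse event and medication dates in main SAP section 6.6 all stay inside the recorded month.

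At stake is the end of recorded exposure in an analysis restricted to seroconversion during ring use. Because the recorded date is what gets printed, a reader of the listings could not see that an earlier date had been used.

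**Working it through.** **Inputs.** The rule is from addendum 4.4. Expected wear of 30 days is from main SAP 9.4.4; the range 30 ± 7, that is 23 to 37 days, and the longer interval classes are from main SAP 9.2. Insertion dates are assumed uniform over the calendar. The plan gives no figure of its own to reproduce.

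**Which month.** I read the month in the rule as the recorded removal month. Reading it as the insertion month does not help, because the result could then never be later than the insertion month.

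**Condition for failure.** Let w be the days of wear and d the true day of the month of removal. For w of 28 or more, insertion + 28 days equals the true removal date minus (w − 28) days. This falls before the first of the recorded month when d ≤ w − 28. While w − 28 is no longer than the shortest month, that is (w − 28) days in each of 12 months, so:

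- share of dates imputed before the recorded month = 12 × (w − 28) / 365
- largest shortfall before the first of the month = w − 28 days (ring removed on the 1st)

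| Wear (days) | w − 28 | Share before recorded month | Largest shortfall (days) |
|---|---|---|---|
| 28 or less | – | 0% | 0 |
| 29 | 1 | 12/365 = 3.3% | 1 |
| 30 | 2 | 24/365 = 6.6% | 2 |
| 37 | 9 | 108/365 = 29.6% | 9 |
| 45 | 17 | 204/365 = 55.9% | 17 |
| 60 | 32 (longer than any month) | 100% | 32 |
| 90 | 62 | 100% | 62 |

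Applying the rule date by date to three years of insertion dates from 1 July 2016 gave the same figures.

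**Average over 23 to 37 days, each equally likely.** Only 29 to 37 days contribute: 1 + 2 + … + 9 = 45. The average is 12 × 45 / (365 × 15) = 540/5475 = 9.9%.

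**Examples (2017).**

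- Inserted 3 March, removed 2 April (30 days), recorded as April: min(31 March, 30 April) = 31 March.
- Inserted 1 March, removed 7 April (37 days), recorded as April: min(29 March, 30 April) = 29 March.
- Inserted 2 January, removed 2 April (90 days), recorded as April: min(30 January, 30 April) = 30 January, 62 days before the true date and 61 before 1 April.

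**With a lower bound.** Using max(first day of recorded month, min(insertion + 28 days, last day of recorded month)), no imputed date fell outside the recorded month at any wear time tested from 21 to 90 days. The three examples all become 1 April.

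**The case against.** The arithmetic is not in dispute. The objection concerns consequence, and most of it stands.

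A reader might infer that women known to be wearing a ring will be coded as off product and lose phenotyping. The documents do not support that. Addendum 3.2 excludes women by seroconversion at the Exit Visit together with RNA status at the last product use visit, with no removal date in the criterion. Main SAP 9.3.1 settles on-product infection by retrospective PCR and physician assessment. The off-use marker in the addendum listings has no stated source variable. No addendum shell displays a last-exposure date; those that use one (Table 14.3.7.11, Listing 16.2.8.15) belong to the main SAP, where the programmer's note to Table 14.3.7.11 gives a different rule. Nor is there support for inferring that the affected women had prolonged low drug exposure.

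The trigger may also be rare. Under protocol 5.4.3, reactive rapid tests lead to last-product-use procedures, which include ring removal at the centre and so normally a dated visit. The longest interval classes in main SAP 9.2 describe all rings, not the last ring of women who seroconverted. At 30 days of wear the shortfall is at most 2 days.

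Finally, the branch does not err only towards early dates. A ring inserted on 1 March and removed on 5 March, with only March recorded, is imputed to 29 March, 24 days late. A lower bound leaves that error untouched.

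None of this defends a rule that overrides a known month. Partial ring dates are also foreseen: a footnote to Listing 16.2.5.2 in the main SAP says how they are handled in the adherence rate.

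**Conclusion.** The rule is wrong as written, and the point is minor. From 29 days of wear, the day-missing branch can place last ring removal before the month in which it was recorded, ending exposure too early. The size depends on wear: small at the intended 30 days, up to 9 days at the edge of the permitted range, and certain to occur at 60 days or more. These shares assume uniform insertion dates and fixed wear times; the 23 to 37 day average also assumes each wear time is equally likely. They apply only to removal dates with a known month and a missing day, whose number is not given.

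Any derivation that uses the imputed date could be affected, for example seroconversion during versus off ring use. The addendum does not say which derivations those are, so an actual change in any woman's classification is not shown.

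**What to change.** In addendum 4.4, replace the day-missing branch with: max(first day of recorded month, min(last insertion + 28 days, last day of recorded month)). Leave the rest of 4.4 unchanged. The cost is one clause and one line of code, and no imputed date that already lies inside the recorded month is altered.
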